2. STUDY OBJECTIVES AND ENDPOINTS

2.1 Primary Objective and Endpoint

Primary Objectives	Primary Endpoints
Safety: To evaluate the safety of IV infusions of SYNT001 at different dose levels and dosing regimens in subjects with pemphigus (vulgaris or foliaceus)	Safety: The evaluation of SYNT001 safety based on vital signs, physical examinations, electrocardiograms (ECGs), clinical safety laboratory tests, the incidence of adverse events (AEs), treatment-emergent adverse events (TEAEs) and serious adverse events (SAEs) summarized by dose and dosing regimen, severity, and relationship to study drug
Dose Selection: To determine a Minimum Effective Dose (MED) of SYNT001 as assessed by (i) total IgG level nadir and (ii) the proportion of subjects that meet the criteria for response by Pemphigus Disease Area Index total activity score (PDAI)	Dose Selection: The determination of dose and dosing regimen of SYNT001 that achieves (i) total IgG level nadir decrease by $\geq 60\%$ and $\leq 90\%$ from baseline and (ii) a PDAI total activity score of $\geq 50\%$ reduction from baseline to allow further clinical development in subjects with pemphigus (vulgaris or foliaceus)

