3. STUDY OVERVIEW

3.1 Overall Study Design and Treatment Assignment

This is a multicenter, open-label safety study to determine the dose regimen of SYNT001 administered IV in subjects with pemphigus (vulgaris or foliaceus). Up to 8 subjects with a

diagnosis of pemphigus (vulgaris or foliaceus) will receive SYNT001 10 mg/kg weekly x 5 doses (Cohort 1). Up to 12 subjects with a diagnosis of pemphigus (vulgaris or foliaceus) will receive SYNT001 30 mg/kg weekly x 3 doses (Loading), followed by SYNT001 10 mg/kg every other week x 5 doses (Maintenance) (Cohort 2).

Subjects in both cohorts will complete the following periods of assessment: Screening, Treatment, and Follow-Up.

The Dose Escalation Committee (DEC) will consist of the Medical Monitor, an Independent Clinical Expert and the Sponsor Medical Lead. The DEC may request that Investigators, other experts, or members within their organization participate in the review. Additional information on the DEC’s responsibilities is provided in Protocol Section 9.5 and the DEC Charter.

An overview of the study cohorts is provided in Table 1.

Table 1. Cohort Overview

Cohort No.	No. of subjects	SYNT001 Dose	No. of Doses	Frequency of Doses
1 ^a	Up to 8	10 mg/kg	5	NA
2 ^b	Up to 12	Loading: 30 mg/kg ^c Maintenance: 10 mg/kg ^c	3 ^c 5 ^c	Weekly ^c Every other week ^{c, d}

- a. No more than 3 subjects with pemphigus foliaceus may be enrolled
- b. Two or fewer subjects with pemphigus foliaceus may be enrolled
- c. The dose, number of doses, and frequency of doses in Cohort 2 will be confirmed based on review of safety and PD evaluations, including but not limited to, dose-limiting toxicities, AEs, TEAEs, SAEs, and total IgG levels. Following Sponsor review of emerging safety, PD and efficacy data, the Loading dose may be reduced to 20 or 10 mg/kg weekly and/or the Maintenance dose may be increased to 20 or 30 mg/kg every other week and/or dose frequency may be increased to weekly.
- d. Ongoing safety and PD evaluations may result in modification of the dose and dosing regimen in Cohort 2. See Protocol APPENDIX 5 for the corresponding visit schedule.

The duration of subject participation for each cohort is as follows:

Cohort	Screening	Treatment	Follow-up	Maximum Total	
				Days	Weeks
1	≤14 days	28 days	84 days	126 days	18 weeks
2	≤14 days	84 days	56 days	154 days	22 weeks

Subjects will be enrolled at staggered intervals to facilitate adequate safety evaluation before dosing of subsequent subjects.

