4.1 General Design

All clinical data captured will be provided in data listings. Subject disposition, demographic information, and baseline characteristics will be presented. Baseline will be defined as the last value obtained prior to the first dose of study drug. Results will be summarized by dose and dosing regimen (cohort), and in total. Any discrepancy between treatment to be given and treatment received will be accounted for in these displays.

Continuous data will be summarized using descriptive statistics: number of subjects (N), number of observations (n), mean, median, standard deviation (SD), minimum, and maximum.

Categorical data will be summarized using frequencies and percentages. When categorical data will be presented, the percent will be suppressed when the count is zero to draw attention to the non-zero counts. The denominator for all percentages, unless otherwise specified, will be the number of subjects in the specified analysis population.

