4.8 Dose Selection Analyses

The evaluation of SYNT001 based on total IgG levels and responses on the PDAI total activity score from baseline will be summarized using descriptive statistics. The number and proportion of patients that achieve the following criteria will be summarized (i) total IgG level nadir decrease by $\geq 60\%$ and $\leq 90\%$ from baseline and (ii) a PDAI total activity score of $\geq 50\%$ reduction from baseline to allow further clinical development in subject with pemphigus (vulgaris or foliaceus).

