- l. Immunoglobulins (IgG, IgA, IgM) and IgG subtypes (IgG 1-4): Collected for measurements of IgG, IgG subtypes (IgG1-4), IgA, and IgM at every visit. On dosing days, samples are collected prior to infusion of study drug. See Protocol Section 7.5.5 for additional information.
- m. Exploratory pharmacodynamic samples (C3 and AECA): Collected pre-dose when collected on dosing days. See Protocol Section 7.5.5 for complete information.
- n. Buccal samples to be collected pre-dose.
- o. Immunophenotyping by flow cytometry for measurement of CD3+CD4+ T, CD3+CD8+ T, monocytes, natural killer (NK) cells, and B cells. Collect samples pre-dose on dosing days.
- p. Photographs of all active lesions taken pre-dose on dosing days. Subjects who begin a steroid taper will have additional photographs taken at the clinic visit during which the decision to begin the taper is made.
- q. Subjects whose total IgG is not within 30% of their Day 0 baseline value and not above 500 mg/dL at the Day 140 visit will be referred for further management.

Table 4. Timing Window Allowances for PK/PD Sampling, ECG, and Vital Sign Measurements at Dosing Visits

Time Point	Tolerance Window	
	Cohort 1	Cohort 2
Pharmacokinetic Sampling		
0 hour	-240 minutes to 0 hour	-240 minutes to 0 hour
5 minutes post end-of-infusion	±5 minutes	±5 minutes
1 hour post end-of-infusion	N/A	±15 minutes
2 hour post end-of-infusion	±15 minutes	±15 minutes
4 and 6 hours post end-of-infusion	±15 minutes	N/A
24 hours (1 day) post end-of-infusion	±60 minutes	N/A
48 hours (2 days) post end-of-infusion	±120 minutes	N/A
Pharmacodynamic Sampling		
0 hour	-240 minutes to 0 hour	-240 minutes to 0 hour
24 hours (1 day) post end-of-infusion	±60 minutes	N/A
48 hours (2 days) post end-of-infusion	±120 minutes	N/A
ECG		
5 minutes post end-of-infusion	±10 minutes	±10 minutes
Vital Signs^a		
0 hour	-240 minutes to 0 hour	-240 minutes to 0 hour
15, 30, and 45 minutes after start of infusion	±5 minutes	±5 minutes
At completion of the infusion	±10 minutes	±10 minutes
30 minutes, 1 and 2 hours post end-of-infusion	±10 minutes	±10 minutes

Abbreviations: ECG = electrocardiogram; N/A = not applicable; PD = pharmacodynamics; PK = pharmacokinetic.

a. Vital signs to include blood pressure, pulse rate, respiratory rate, oral temperature, and pulse oximetry.

Table 5. Pharmacodynamic Assessments

Parameter	Collection Time Points	
	Cohort 1	Cohort 2 ^a

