Immunoglobulins: 
 • IgG • IgG subtypes (IgG1-4) • IgA • IgM 	Screening and Days 0, 1, 2, 5, 7, 12, 14, 19, 21, 28, 29, 30, 33, 42, 56, 84, and 112	Screening and Days 0, 7, 14, 28, 42, 56, 70, 84, 91, 112, and 140

 • Circulating immune complexes (CIC) 	Days 0, 5, 7, 12, 14, 19, 21, 28, 33, 42, 56, 84, and 112	Days 0, 7, 14, 28, 42, 56, 70, 84, 91, 112, and 140

 • Albumin 	Screening and Days 0, 7, 14, 21, 28, 33, 42, 56, 84, and 112	Screening and Days 0, 7, 14, 28, 42, 56, 70, 84, 91, 112 and 140

 • Anti-Dsg (1 and 3) antibody titers 	Screening and Days 0, 7, 14, 33, 56, 84, and 112	Screening and Days 0, 7, 14, 28, 42, 56, 70, 84, 91, 112, and 140

 • C3 and AECA levels by indirect immunofluorescence 	Days 0, 14, 33, 56, 84, and 112	Screening and Days 0, 7, 14, 28, 42, 56, 70, 84, 91, 112, and 140

 • Exploratory biomarkers (RNAseq, urine IgG)^b 	Days 0, 14, 33, 56, 84, and 112	Days 0, 28, and 91

 • Immunophenotyping by flow cytometry for measurement of T cells, monocytes, NK cells, and B cells 	Days 0, 28, and 56	Days 0, 28, and 91

 • Exploratory biomarker (FCGR2A SNP, via buccal swab) 	Day 0	Day 0

 • Exploratory pemphigus immune response biomarkers 	Days 0, 5, 7, 12, 14, 19, 21, 28, 33, 42, 56, 84, and 112	Days 0, 7, 14, 28, 42, 56, 70, 84, 91, 112, and 140

^a Ongoing safety and PD evaluations may result in modification of the dosing regimen from every other week to weekly. See Protocol APPENDIX 5 for the corresponding visit schedule.

^b Urine IgG collected in Cohort 1 only.

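### The primary IgG-nadir count takes a minimum over unequal sampling schedules: Cohort 2 has no scheduled sample earlier than 7 days after a dose, so its nadir is likely recorded too shallow, and one achieved count hides the direction of a miss

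*SAP*

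**What the plan says.** Section 2.1 states the dose-selection part of the primary objective as "To determine a Minimum Effective Dose (MED) of SYNT001 as assessed by (i) total IgG level nadir", together with PDAI response. The matching endpoint asks for a nadir at least 60% and at most 90% below baseline. Section 4.8 makes this a descriptive count: "The number and proportion of patients that achieve the following criteria will be summarized". It does not say which visits contribute to the nadir. Section 4.1 adds: "Results will be summarized by dose and dosing regimen (cohort), and in total".

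The samples are set in Appendix A, Table 5. For immunoglobulins:

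- Cohort 1: "Screening and Days 0, 1, 2, 5, 7, 12, 14, 19, 21, 28, 29, 30, 33, 42, 56, 84, and 112".
- Cohort 2: "Screening and Days 0, 7, 14, 28, 42, 56, 70, 84, 91, 112, and 140".

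Table 3, footnote l says of Cohort 2: "On dosing days, samples are collected prior to infusion of study drug". Table 2, footnote k applies the same rule to the Cohort 1 dosing days.

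**The concern.** An observed minimum depends on how many samples are taken and on how soon they follow a dose. If IgG is lowest a few days after each infusion and then recovers, a schedule made of pre-dose troughs misses the lowest point and a schedule with early post-dose draws does not. The same row in the 4.8 table would then describe two different quantities.

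This criterion is half of the dose-selection endpoint, and there are only two cohorts from which to judge a minimum effective dose. Reading the two proportions side by side is how the table will be used, even though no test is planned. A too-shallow reading can turn a true fall above 60% into a failure, or a true fall above 90% into a pass.

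The form of the summary adds a separate problem. A subject below 60% and a subject above 90% both count as not achieving the criterion, yet they point in opposite directions for dose selection.

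**Working it through.** The SAP states no figure on this point, and Section 5 reports no sample-size calculation, so there is nothing to reproduce. The check has three steps.

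**1. Time since the previous dose.** Dosing days come from Tables 2 and 3: Cohort 1 on Days 0, 7, 14, 21, 28; Cohort 2 on Days 0, 7, 14, 28, 42, 56, 70, 84. Lag = sampling day minus the last earlier dosing day, since dosing-day samples are pre-dose.

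| Lag (days) | Cohort 1 sampling days | Cohort 2 sampling days |
|---|---|---|
| 1 to 5 | 1, 2, 5, 12, 19, 29, 30, 33 | none |
| 7 | 7, 14, 21, 28 | 7, 14, 91 |
| 14 | 42 | 28, 42, 56, 70, 84 |
| 28 or more | 56, 84, 112 | 112, 140 |
| Total | 16 | 10 |

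Days 7, 14 and 42 match on both study day and lag. The third loading dose (Day 14) is followed by no Cohort 2 sample until Day 28.

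The visit windows in Table 3 loosen this a little. Actual Cohort 2 lags can be 6 to 8 days at Day 7, 5 to 9 days at Day 14 and below 7 days at Day 91. They stay at 8 days or more from Day 28 to Day 84.

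**2. Possible size.** All inputs here are assumptions, because the SAP gives no kinetics. IgG level R (baseline 1) follows dR/dt = k − k(1 + E)R, with k = ln 2 / 21 days and E = Emax × C / (EC50 + C). C is the sum of the mg/kg doses, each decaying with half-life 0.5, 1 or 2 days. Emax is 4, 8 or 15 and EC50 is 0.5 or 2, giving 3 × 3 × 2 = 18 scenarios. Shortfall = true maximum fall minus the largest fall on a scheduled sampling day.

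| Half-life, Emax, EC50 | Cohort 1 true → recorded | Cohort 2 true → recorded | Cohort 2 shortfall |
|---|---|---|---|
| 0.5, 8, 2 | 59.0% → 58.9% | 64.7% → 50.5% | 14.2 |
| 1, 4, 2 | 56.7% → 55.8% | 61.2% → 51.3% | 9.9 |
| 1, 15, 2 | 86.4% → 86.0% | 90.3% → 84.7% | 5.6 |
| 2, 8, 0.5 | 87.4% → 87.2% | 87.9% → 86.3% | 1.6 |
| 2, 15, 0.5 | 93.0% → 92.9% | 93.5% → 93.1% | 0.4 |

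Over all 18 scenarios the shortfall is 0.0 to 0.9 points in Cohort 1 and 0.4 to 14.2 in Cohort 2, and it is larger in Cohort 2 every time. In the first two rows a true pass of the 60% limit is recorded as a failure. In the third, a true fall above 90% is recorded as inside the range.

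As a diagnostic of cause, adding model readings 5 days after each Cohort 2 dose and on Day 21 cuts its shortfall to 0.0 to 4.2 points. The gap therefore comes mainly from sample timing.

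**3. Noise alone.** Suppose a flat true fall of 55% and a CV of 10% (both assumed), and count samples up to 7 days after the last dose: 12 in Cohort 1 and 8 in Cohort 2. The expected minimum is 0.837 and 0.858 of the true level. The recorded falls are 100 × (1 − 0.45 × 0.837) = 62.3% and 100 × (1 − 0.45 × 0.858) = 61.4%. Noise deepens the minimum in both cohorts, against the timing effect, but leaves Cohort 1 deeper by about 0.9 points.

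**The case against.** Several stronger readings are tempting, and the document does not support them.

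- *Cohort 2 is never sampled within 7 days of a dose.* Days 7, 14 and 91 are nominally at 7 days, and the windows allow earlier draws. The accurate statement is that none is scheduled earlier than 7 days.
- *The Cohort 2 nadir is understated and the dose comparison biased, as a fact.* The SAP gives neither drug nor IgG kinetics. In three of the slow-kinetics scenarios the shortfall is only 0.4 to 1.6 points. No formal comparison is planned, and the upper limit means a shallower reading can also raise the Cohort 2 pass rate.
- *A true 65% fall would be recorded as 48%.* This follows if the trough is 5 days after the third loading dose (Day 19), the deficit recovers with a 21-day half-life and only Day 28 is read: 65 × 2^(−9/21) = 48.3%. But the nadir uses every visit. Under the same assumptions, a 65% fall reached 5 days after a dose and sampled 2 days later, as at Day 14 or Day 91, is recorded as 65 × 2^(−2/21) = 60.8% (58.9% to 61.9% for half-lives of 14 to 28 days).

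The SAP also covers part of the need already. Section 4.9.2 summarises IgG by cohort and visit, with minimum and maximum, and plots percent change. Sections 4 and 4.1 list all data, and there are at most 20 subjects. The collection schedule belongs to the protocol, and Cohort 2 may move to weekly dosing (Table 5, footnote a).

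These points limit the size and severity. They leave standing that 4.8 does not define the sample set for a primary criterion whose schedules differ. Per-visit summaries do not give a lag-matched count against the limits, nor the direction in which subjects missed them.

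**Conclusion.** The point holds in a limited form. That the schedules differ is plain from the tables: 16 scheduled samples against 10, and 8 against none earlier than 7 days after a dose. That the Cohort 2 nadir is recorded too shallow is likely, but it rests on IgG recovering between doses. The range of 0.4 to 14.2 points, against 0.0 to 0.9 in Cohort 1, is conditional on the assumed turnover models and is not an estimate for this drug. The effect on the proportion meeting the criterion has no fixed sign. The merging of falls below 60% with falls above 90% needs no assumption.

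Severity is moderate: the reading of a primary endpoint is affected, but the analysis is descriptive, the data are listed, and the remedy needs no new samples.

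**What to change.** In Section 4.8:

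- (a) Define the nadir as the *lowest observed* total IgG within cohort, name the samples that contribute, and state that the schedules differ, so the two proportions are not like for like.
- (b) Add a sensitivity summary by subject: percent IgG fall and threshold category at Days 7 and 14, where both cohorts are 7 days after a dose, with Day 42 (14 days after a dose in both) as support. A minimum over shared calendar days is no substitute, because it is not lag-matched: Day 28 is 7 versus 14 days after a dose in Cohorts 1 and 2, Day 56 is 28 versus 14, and Day 84 is 56 versus 14.
- (c) Replace the single achieved count with three categories by cohort: <60%, 60-90% inclusive, and >90%.

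If Cohort 2 moves to weekly dosing, choose the matched days from that schedule.

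The cost is SAP wording and one extra table from data already planned, best settled before the programming specifications are finalised (Section 6). The limit is that Days 7 and 14 precede any effect of the third loading dose, and Day 42 comes 28 days after it. The matched days therefore do not cover the peak loading effect and cannot recover an unsampled nadir.

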Appendix B: Imputation Rules for Missing Dates

Imputation Rules for Missing Prior/Concomitant Medication Dates

Imputation rules for missing or partial medication start/stop dates are defined below:

1. Missing or partial medication start date:
 - If only DAY is missing, use the first day of the month.
 - If DAY and Month are both missing, use the first day of the year.
 - If DAY, Month and Year are all missing, use a date before the first dose date (in practical, use Jan. 01, 2000 to impute).
2. Missing or partial medication stop date:
 - If only DAY is missing, use the last day of the month.
 - If DAY and Month are both missing, use the last day of the year.
 - If DAY, Month and year are all missing, assign 'continuing' status to stop date (in practical, use Dec. 31, 2050 to impute).

Imputation rules for missing or partial AE start date are defined below:

If only Day of AE start date is missing:

If the AE start year and month are the same as that for the first dose date, then:

- If the full (or partial) AE end date is NOT before the first dose date or AE end date is missing, then impute the AE start day as the day of first dose date; otherwise, impute the AE start day as 1.
- Otherwise, impute the AE start day as 1.

Compare the imputed AE start date with Treatment-Emergent period to determine whether the AE is pretreatment AE, TEAE or post-treatment AE.

If Day and Month of AE start date are missing:

If AE start year = first dose year, then:

- If the full (or partial) AE end date is NOT before the first dose date or AE end date is missing, then impute the AE start Month and Day as the Month and Day of first dose date; otherwise, impute the AE start Month as January and the Day as 1.
- Otherwise, impute the AE start MONTH as January and the DAY as 1.

Compare the imputed AE start date with Treatment-Emergent period to determine whether the AE is pretreatment AE, TEAE or post-treatment AE.

If Year of AE start date is missing:

If the year of AE start is missing or AE start date is completely missing then query site with no imputation. Also compare the full (or partial) AE end date to the first dose date. If the AE end date is before the first dose date then the AE should be considered as a pretreatment AE. Otherwise, the AE will be considered as TEAE.
